Appendix 25: Outreach Talking Points

Introduction:

- Briefly introduce yourself and express gratitude for the person's time.
- Mention that you'd like to share information about a valuable opportunity called the ImmunoCARE Study, which does not involve any treatment.

Study Purpose:

- Explain that the ImmunoCARE Study is a collaboration between Scripps Research and Cue Health.
- Explain that the study aims to understand and improve COVID-19 outcomes specifically for immunocompromised individuals and those aged 65 and above.
- Emphasize the study does not involve treatment.

Target Population:

- Highlight the increased risk for severe outcomes from COVID-19 in individuals with compromised immune systems or over the age of 65.
- Mention the specific conditions that make someone eligible, such as Symptomatic HIV,
 Graft versus host disease, Immunoglobulin deficiency, etc.

Study Activities:

- Explain the two groups within the study: one group continues normal testing and care-seeking, while the other receives at-home COVID-19 tests and additional support.
- Emphasize that all participants, regardless of group, will be asked to complete monthly surveys about COVID-19 exposure, infection, and hospitalization.

Innovative Approaches:

- Discuss the innovative aspects of the study, including at-home testing, telemedicine consultations, and rapid medication delivery.
- Stress the importance of finding practical and effective ways to support individuals in managing COVID-19.

Participant Appreciation:

- Express gratitude for the participant's potential contribution to the research.
- Mention that eligible participants will receive compensation in the form of Amazon gift cards as a token of appreciation for their time throughout the study.

Joining the Study:

- Share the official study website link: https://immunocare.scripps.edu/
- Provide information on how individuals can check their eligibility and sign up for the study.

Impact of Participation:

 Stress the potential impact of their involvement, highlighting that their contribution could significantly influence our understanding and management of COVID-19 in vulnerable populations.

Questions and Concerns:

- Encourage participants to ask any questions they may have about the study.
- Provide referrals for health and social services when participants describe barriers to participation related to social determinants of health.
- Provide your contact information (email or phone number) or direct them to the study website or email address ([contact]) for more detailed information.

Closing:

- Thank them for considering participation in the ImmunoCARE Study.
- Reiterate the importance of their potential role in advancing crucial research efforts.

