The DTC is also home to advanced data analytics that incorporate machine learning and other artificial intelligence approaches. DTC has launched several IRB-approved digital studies that address diabetes (PROGRESS), maternal health (PowerMOM) and sleep (Refresh).

In March 2020, Scripps launched the Digital Engagement & Tracking for Early Control, & Treatment (DETECT) study, an app-based research platform that allows for consented

participants to share their wearable device data, self-reported symptoms, test results, vaccine information, and to optionally connect electronic health record (EHR) data. DETECT builds from our team's prior work utilizing wearable device data to monitor influenza-like-illnesses at a state level (Radin, Wineinger, Topol, & Steinhubl, 2020). DETECT aims to provide a deeper understanding of physiological and behavioral changes associated with viral illness, including COVID-19 with the goal of ultimately improving real-time digital disease detection. DETECT has enrolled over 40,000 participants from across the country. The observational data collected has led to several findings including the ability to discriminate between COVID-19 and other illnesses among symptomatic individuals (Quer, Radin, et al., 2021; Gadaleta et. al., 2021) and a prolonged deviation of daily resting heart rate (RHR) for SARS-CoV-2 positive individuals (Radin et al., 2021). Another analysis showed deviation in resting heart rate post-vaccination with observed differences between doses as well as between types of mRNA vaccines (Quer, Gadaleta, et al., 2022). Most recently, the DETECT team published and confirmed the utility of wearable device data in the early detection of COVID-19 and other acute respiratory infections (Radin et al., 2022).

Scripps DTC and Cue Health, in a new collaborative partnership, will combine their expertise in portable COVID-19 testing and direct to participant research to address the needs of the immunocompromised community.

Purpose

To examine whether a combination of at-home nucleic acid amplification tests, on-demand telemedicine, and delivery of Paxlovid within hours of testing positive for COVID-19, can reduce severe outcomes and hospitalization of immunocompromised patients. We will also analyze whether these efforts lower the cost of care compared to standard of care.

Study Design

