We plan to conduct a randomized control trial with 10,000 participants. Participation will last for a minimum of 4months and maximum of 8 months, depending upon COVID-19 case rates. Half of participants will be randomized to the control group and continue their existing testing and healthcare practices. The remaining participants will be randomized into the intervention arm. Participants in the intervention will receive one Cue Cartridge Reader for the duration of the study and up to 10 Cue COVID Molecular tests per month for their own

use and to share with others who could expose them to COVID-19 (e.g. close contacts). In the case that a Cue Flu+COVID Molecular Test is available through FDA EUA or other authorization, participants may be provided this multiplex test in lieu of the Cue COVID Molecular Test.

[figure not shown]
Table 1. Summary of Study Arms

Study Arm	Number of participants	COVID-testing practice
Control	5,000	None within this study
Intervention Arm	5,000	10 Cue tests per month to participants' for self and close contact use. Option to utilize Cue's telehealth and Rx delivery.

All intervention participants will be asked to test themselves if they are exposed or when symptoms arise. The primary outcome will be the number of hospitalizations that will be assessed from survey and claims data. We will also compare infection rates, ICU admissions, ED visits, deaths and cost of care between the control and intervention group. Our hypothesis is that access to high sensitivity portable molecular testing and subsequent antiviral treatment will significantly decrease hospitalization and thereby the cost of care.

Interested individuals will access the study via the MyDataHelps platform by web or app to complete the eligibility and informed consent process. Within the MyDataHelps experience, participants will complete study activities such as surveys and optional sharing of claims data. Participants who are randomized to the intervention group will have the option to use Cue Care should they test positive for COVID-19. In the case that the COVID Flu+COVID test is available, the intervention group will also have the option to use Cue Care should they test positive for Influenza. Cue Care contracts licensed Healthcare providers to deliver telemedicine and treatment for COVID-19.

Figure 1: Participant Flow

Study Population

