Heading (claims): **Diagnosis Confirmation** Body: The claims data from your health plan indicate a previously diagnosed condition that we need to learn more about for the purposes of this study. Please upload a document confirming your diagnosis on the next screen. This can be a doctor's note, a screenshot of your EHR diagnosis list, lab work, test results or medication list. Accepted file types are [list of file types]. If your document is another type, please email it to the study team at [contact] **Button Text:** Next Heading (no claims): **Diagnosis Confirmation** Body: Thank you for your participation! Please upload a document confirming your diagnosis or age on the next screen. This can be a doctor's note, a screenshot of your EHR diagnosis list, lab work, test results or medication list. Accepted file types are [list of file types]. If your document is another type, please email it to the study team at [contact] **Button Text:** Next

Heading: [None]

Body: [None]

Button Text: Capture or Upload Image
Heading: Thank you
Body: Thank you for confirming your medical information. We will be reviewing the document you uploaded and will notify you when we are ready for you to continue with the study.
Button Text: Done
Heading: Document Review
Body: Our research coordinator is currently reviewing the document you uploaded confirming your diagnosis or age. This process can take a few business days, we appreciate your patience.
No further action is required on your part. We will notify you once we complete our review so you can continue with the study.
Button Text: Done
Heading: Baseline survey
Body: Help us learn about other diagnoses and understand any differences between demographic groups, such as income, race, ethnicity, and age.
Button Text: Next
[Baseline survey questions here; see Appendix 3]

Pre-conditions: Participant randomized into treatment arm
Heading: Thank you
Body: Thank you for sharing this information with the study team.
You have been randomized to the treatment group.
As such, the next step is to register an account with Cue Health and download their app on your smartphone. You will also order your testing kit through the mobile app.
Continue to the next task for additional instructions.
Button Text: Done
Pre-conditions: Participant randomized into control arm
Heading: Thank you
Body: Thank you for completing all of the onboarding activities.
You have been randomized to the control group.

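### The outreach talking points tell staff to say the study involves no treatment, which contradicts the tested package, the staff's own handout and a later bullet in the same script

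*Combined protocol and SAP*

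**What the plan says.** Appendix 25 (Outreach Talking Points) makes the statement twice. The Introduction has staff describe a study "which does not involve any treatment", and the Study Purpose block adds "Emphasize the study does not involve treatment". Further down, the Innovative Approaches block asks the same staff to talk about "at-home testing, telemedicine consultations, and rapid medication delivery".

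The protocol body describes a treatment pathway. The Purpose section asks whether home testing, "on-demand telemedicine, and delivery of Paxlovid within hours of testing positive for COVID-19, can reduce severe outcomes and hospitalization of immunocompromised patients". The hypothesis in Study Design is that "access to high sensitivity portable molecular testing and subsequent antiviral treatment will significantly decrease hospitalization". Table 1 lists telehealth and prescription delivery as options for the intervention arm. The Intervention Arm section says COVID-19 medication will be prescribed and delivered when clinically indicated, and that participants may instead use another provider or seek no care.

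The Outreach section assigns the Appendix 25 script to outreach staff. It also has the outreach team share the Appendix 4 one-pager and help participants in San Diego County with the consent process and with finding their way around the Cue app.

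**The concern.** A recruitment script should describe accurately what each arm is offered. For the control arm it is fair to say that the study supplies no treatment. For the intervention arm, access to a prescriber and to delivered antiviral medication is one of the named components under test. Staff who follow the script as written tell immunocompromised and older people the opposite, and are asked to stress it.

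The main thing at stake is the accuracy of what people hear before consent, from a team that then helps them through consent. A lesser matter is interpretation: if uptake of the treatment pathway is later examined among people recruited this way, some of them were told that no such pathway was part of the study.

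**Working it through.** This is a comparison of texts, and no stated figure attaches to it.

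**Step 1: what is tested, against what is said.**

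| Place | Position on treatment |
|---|---|
| Purpose | Telemedicine and Paxlovid delivery are part of the tested combination |
| Study Design, hypothesis | Antiviral treatment is named as part of the route to fewer hospitalizations |
| Table 1 | Telehealth and prescription delivery offered as options |
| Intervention Arm | Medication prescribed and delivered when clinically indicated; other care or no care allowed |
| Cue Care | Optional, provided through third-party medical groups |
| Appendix 4 one-pager | Telemedicine and quick medication delivery described |
| Appendix 25, Innovative Approaches | Telemedicine and rapid medication delivery to be discussed |
| Appendix 25, Introduction and Study Purpose | No treatment, stated twice, once with emphasis |

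Only the last row denies treatment. It conflicts with the protocol body, with the handout the same staff share, and with its own script.

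**Step 2: is the statement true in some sense?** The Cue Care section makes the service voluntary and places it with third parties, so the study team itself administers nothing. The script does not draw that distinction. Optional treatment that is offered to one arm and named in the hypothesis is still treatment within the study's intervention.

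**Step 3: who hears it, and when?** The script is used at outreach, before consent and randomization, so people who later enter either arm can hear it. The same team's help with study steps is described for San Diego County, while the explainer video script (Appendix 21) describes nationwide enrollment. The number recruited through outreach is not given.

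**Step 4: does any stated figure depend on it?** The plan states power of 0.76 at about 450 cases per arm. Its inputs are alpha 0.05 (taken as two-sided), a 23.5% hospitalization rate per case in the control arm, and a 30% relative reduction, so 0.235 × 0.70 = 0.1645 in the intervention arm. With a pooled-variance normal approximation:

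- difference = 0.235 − 0.1645 = 0.0705; mean rate = 0.19975
- SE under the null = √(2 × 0.19975 × 0.80025 / 450) = 0.02665
- SE under the alternative = √((0.235 × 0.765 + 0.1645 × 0.8355) / 450) = 0.02655
- z = (0.0705 − 1.96 × 0.02665) / 0.02655 = 0.69, giving power of about 0.754

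The stated power therefore reproduces. It contains no treatment-uptake term and no outreach term, so correcting the script changes nothing in it.

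**The case against.** The strongest defence has three parts.

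- **A narrower meaning.** Staff may have been meant to convey that the study itself gives no drug. Cue Care is voluntary and third-party, and one of the Optum recruitment pieces (Appendix 19) describes Paxlovid as ordered within a person's regular medical care. The in-app screen that says "You have been randomized to the treatment group" adds little against this reading, because there the word is an arm label. The narrower meaning is plausible as intent, but it is not what the script says.
- **Correction before consent.** The one-pager, the landing page (Appendix 13) and the script's own later bullet all mention medication delivery. Consent Procedures provides in-app onboarding and a long-form consent covering purpose, methods, risks, benefits and alternatives. This stands, and it is why the point is minor. The consent pages are not among the text reviewed, so whether they fully cure the message cannot be judged.
- **Little left to protect.** Estimated Duration of Study says the trial is ending early and that the data will be analyzed mainly to characterize the pandemic's effect on this population. This also stands, and it limits the practical gain from any correction.

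A reader might go further and infer that the message lowered use of the treatment pathway, and so diluted the assumed 30% reduction in hospitalizations per case. The documents do not support that. If f is the share of infected intervention participants who came through outreach, and s the fraction of them who lose the whole benefit because of the message, the reduction would be 30% × (1 − s × f). Neither s nor f is given, no passage links the script to later use of Cue Care, and any effect is confined to the outreach share.

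**Conclusion.** The contradiction is real, and Appendix 25 is wrong as written. Two statements in one recruitment appendix deny a component that the Purpose, hypothesis, Table 1 and Intervention Arm text all include, and the script contradicts itself further down. People reached by outreach receive an inaccurate and mixed description before consent.

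Severity is minor. No design, endpoint, sample-size or analysis figure changes, several other materials give the correct picture, and formal consent is a separate step. This assumes that staff used the script as written and that the in-app consent describes the intervention as the protocol does. A reader might also infer that consent was invalid or that the arm contrast was weakened; the documents establish neither.

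**What to change.** Delete both no-treatment statements from Appendix 25. Replace them with the description already given under Intervention Arm and in the explainer video script (Appendix 21). In substance: after a positive test, people in the intervention group may choose a telemedicine consultation and, when clinically indicated, have medication prescribed and delivered; they may instead use their own provider or seek no care. If the intended message was that care is optional and comes from third parties, the script should say that.

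Because the study is ending early, the report should also record that outreach staff were given an inconsistent message, and should bear this in mind when interpreting treatment uptake among outreach-recruited participants. The monthly and end-of-study surveys ask whether COVID-19 medication was prescribed, so some information on uptake exists. The reviewed text does not say whether recruitment source was recorded; if it was not, a sentence in the limitations is enough.

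The cost is two lines of script, a short note to outreach staff and one sentence in the report. The protocol calls the one-pager IRB-approved but does not say so of the talking points, so the sponsor should check whether the change needs submission.

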Appendix 26: FDA Alert Email

SUBJECT LINE:

Do Not Use Cue Health Device

PREHEADER:

Cue Health's COVID-19 Tests Have a Risk of False Results

BODY COPY:

Dear [FIRST NAME],

This is an alert regarding the ImmunoCARE Study. The U.S. Food and Drug Administration (FDA) issued a communication to recommend that patients, caregivers, and health care providers do not use Cue Health's COVID-19 Tests due to an increased risk of false results.

We are determining next steps for the ImmunoCARE Study. In the meantime, please discontinue use of your Cue Health tests. We thank you for your participation and apologize for any inconvenience this may cause.

Take Care,

The ImmunoCARE Study Team

Questions? Reach out to us at [contact]

Appendix 27: FDA Alert Push Notification/SMS

Theme: FDA Alert Push/SMS

Trigger: Push once IRB approved

Title: Don't Use Cue Health Device

Push or SMS copy: Cue Health's COVID-19 Tests Have a Risk of False Results, please

discontinue use

Appendix 28: ImmunoCARE Study Closure

SUBJECT LINE:

The ImmunoCARE Study is Ending

PREHEADER:

Please take your End of Study Survey

BODY COPY:

Dear [FIRST NAME],

We are writing you as a valued participant in the ImmunoCARE study to share important news. We are stopping the ImmunoCARE study early in response to the FDA warning calling for discontinuing use of Cue COVID-19 tests.

The ImmunoCARE study team appreciates your participation and understanding. If you have not done so already, please take your end of study survey and share your claims data. Participants who agree to connect their health claims data will receive a \$30 Amazon gift card as a thank you, while supplies last.

Take Care,

The ImmunoCARE Study Team

Questions? Reach out to us at [contact]
